3 INVESTIGATIONAL PLAN

3.1 Study Design and Duration

This is a phase 1/2 open label study. The first phase of the study will consist of a dose escalation assessment of the safety and tolerability of urelumab administered with nivolumab in subjects with advanced solid tumors or B-cell NHL. The second part of the study will include a 2-stage cohort expansion in multiple tumor types (MEL, NSCLC, SCCHN, DLBCL and FL). Expansion cohorts will be explored at the maximally tolerated dose (MTD), highest administered dose (HAD), or at an alternative dose/regimen as determined by the investigators and the sponsor. The eligibility for the selected tumor types for the cohort expansions are listed in Study Population (Section 3.3).

Subjects will complete up to four periods of the study (Screening, Treatment, Clinical/Safety Follow-up, Survival/Long-term Follow-up): The total time on study for any individual subject is expected to be approximately 3.1 years.

3.1.1 Screening Period

The screening period will last for 28 days. Screening period begins by establishing the subject's initial eligibility and signing of the informed consent form (ICF). Subject is enrolled using the Interactive Voice Response System (IVRS).

3.1.2 Treatment Period

The Treatment Period will consist of up to 6 treatment cycles. Each cycle is 8 weeks for a total of 48 weeks. Nivolumab will be given every 2 weeks; urelumab will be given every 4 weeks. Subjects

completing approximately 48 weeks of initial treatment with ongoing disease control (CR, PR or SD) will be followed to monitor the duration of their disease control and may be eligible for retreatment if their disease progresses within 12 months following treatment discontinuation (see Protocol [Section 4.5.8](#) for retreatment).

Treatment cycles are comprised of 4 doses of nivolumab per cycle and 2 doses of urelumab per cycle. Nivolumab will be administered on Days 1, 15, 29, and 43 and urelumab will be administered on Days 1 and 29 of each treatment cycle depending on the treatment cohort. On days where both study drugs are given, nivolumab will be given first followed by urelumab at least 30 minutes after completion of the nivolumab infusion.

Following each treatment cycle, the decision to treat a subject with additional cycles of study therapy, up to a maximum of 6 cycles, will be based on tumor assessment (evaluation performed between Days 49 and 56 of each cycle and completed before the first dose in the next cycle). Tumor progression or response endpoints will be assessed using RECIST 1.1 criteria for solid tumors ([Appendix 1](#)) and revised International Working Group (IWG) Criteria for non-Hodgkin Lymphoma⁷³ ([Appendix 2](#)) for lymphomas. Treatment beyond initial investigator-assessed progression (either clinical or radiographic) is permitted only if the subject has an investigator-assessed clinical benefit and is tolerating study drug. Subjects with a response of unconfirmed PD, SD, PR, or CR at the end of a given cycle will continue to the next treatment cycle. Subjects will generally be allowed to continue study therapy until the first occurrence of either: 1) completion of the maximum number of cycles, 2) confirmed PD, 3) clinical deterioration suggesting that no further benefit from treatment is likely, 4) intolerance to therapy; or 5) the subject meets criteria for discontinuation of study therapy as outlined in protocol [Sections 3.5](#) and [4.5.7](#). Individual subjects with confirmed CR (or a stable and confirmed PR which, in the investigator's opinion, represents the maximum expected benefit for the subject) will be given the option to discontinue study therapy prior to 12 months on a case by case basis after specific consultation and agreement between the investigator and BMS MM in settings where benefit/risk justify discontinuation of study therapy.

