3.5 Discontinuation of Subjects from Treatment

Subjects MUST discontinue investigational product (and non-investigational product at the discretion of the investigator) for any of the following reasons:

- Subject's request to stop study treatment and/or participation in the study;
- Any clinical adverse event (AE), laboratory abnormality, or intercurrent illness which, in the opinion of the investigator indicates that continued participation in the study is not in the best interest of the subject;
- Termination of the study by Bristol-Myers Squibb (BMS);
- Loss of ability to freely provide consent through imprisonment or involuntary incarceration for treatment of either a psychiatric or physical (eg, infectious disease) illness;
- Pregnancy;
- Documented and confirmed disease progression as defined by RECIST or IWG criteria (see Appendices 1 and 2) unless subject meets criteria for treatment beyond progression (See [Section 3.5.1](#));
- Clinical deterioration while receiving active study therapy that in the opinion of the investigator indicates that continued participation in the study is not in the best interest of the subject;
- Discretion of the investigator;
- Inability to comply with the protocol requirements;
- Protocol defined reasons for discontinuation (see [Section 4.5.7](#)).

The investigator must notify the BMS Medical Monitor/designee in the event a female subject becomes pregnant within 24 hours and submit information to WWS on the pregnancy form within 24 hours. The study drug should be discontinued after pregnancy has been confirmed.

All subjects who discontinue should comply with protocol specified follow-up procedures as outlined in [Table 5.1-3](#). The only exception to this requirement is when a subject withdraws consent for all study procedures or loses the ability to consent freely (ie, is imprisoned or involuntarily incarcerated for the treatment of either a psychiatric or physical illness).

If study drug is discontinued prior to the subject's completion of the study, the reason for the discontinuation must be documented in the subject's medical records and entered on the appropriate case report form (CRF) page.

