3.5.1 Treatment Beyond Disease Progression

As described in [Section 1.1.2](#) accumulating evidence indicates a minority of subjects with solid tumors treated with immunotherapy may derive clinical benefit despite initial evidence of PD. Subjects will be permitted to continue on treatment beyond initial RECIST 1.1 defined PD, or progression defined by relapsed disease (after CR) or progressive disease (after PR, SD) per 2007 IWG criteria, as long as they meet the following criteria:

- Investigator-assessed clinical benefit, and do not have rapid disease progression;
- Continue to meet all other study protocol eligibility criteria;
- Tolerance of study drug;
- Stable performance status;
- Treatment beyond progression will not delay an imminent intervention to prevent serious complications of disease progression (eg, CNS metastases);
- Subject provides written informed consent prior to receiving any additional urelumab/nivolumab treatment, using an ICF describing any reasonably foreseeable risks or discomforts, or other alternative treatment options.

The assessment of clinical benefit should take into account whether the subject is clinically deteriorating and unlikely to receive further benefit from continued treatment. All decisions to continue treatment beyond initial progression must be discussed with the BMS Medical Monitor and an assessment of the risk/benefit of continuing with study therapy must be documented in the study records. Subjects will be re-consented to explain the rationale for this ongoing treatment.

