### 4.2 Secondary Endpoints

#### 4.2.1 Preliminary Antitumor Activity

Tumor assessments will be performed every 8 weeks ( $\pm$  1 week) during the treatment period (Cycle 1 Day 1 through Cycle 6 Day 56), and at planned timepoints during the clinical follow-up period. In addition, subjects who discontinue study drug for reasons other than progression will continue to have tumor assessments completed every 12 weeks for the first year and then continue to receive scans per standard of care guidelines for follow-up or at a minimum of every 6 months until disease progression or withdrawal of consent.

Changes in tumor measurements and tumor response will be assessed by the investigator using the Response Evaluation Criteria in Solid Tumors (RECIST) version 1.1 for subjects with solid tumors and using the revised International Working Group (IWG) Criteria for subjects with B-cell NHL and Follicular Lymphoma. Investigators will also report the number and size of new lesions that appear while on-study. Endpoints will be defined based on all available tumor assessments.

The following set of efficacy study-level endpoints will be used.

- **Objective Response Rate (ORR):** The total number of subjects whose best overall response (BOR) is either a complete response or partial response for solid tumors and complete remission or partial remission for B-cell NHL, divided by the total number of subjects in the population of interest. Hereafter, complete response for solid tumors and complete remission

for B-cell NHL will both be referred to as complete response (CR); partial response for solid tumors and partial remission for B-cell NHL will both be referred to as partial response (PR).

- Best Overall Response: The subject's best response designation over the study as a whole, recorded between the date of first study drug administration and the date of objectively documented progression or relapse per RECIST 1.1 or IWG, with subsequent confirmation, or date of subsequent anti-cancer therapy, whichever occurs first in the study.
  - ◆ A minority of subjects may continue treatment beyond confirmed progression or relapse, as described in Protocol Section 3.5.1. For these subjects, the BOR should be determined based on response designations recorded up to the time of the initial RECIST 1.1 defined progression or IWG defined relapse or progressive disease.

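### Protocol 3.5.1 sets six criteria, including written consent, for dosing past an initial progression; Protocol 3.1.2 gives two, and Protocol 3.5 and SAP 4.2.1 invoke 3.5.1 only at confirmed progression

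*Protocol*

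**What the plan says.** Four places deal with a subject whose scan shows progression.

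- **Protocol 3.1.2.** Treatment beyond initial investigator-assessed progression "is permitted only if the subject has an investigator-assessed clinical benefit and is tolerating study drug". The next sentence reads "Subjects with a response of unconfirmed PD, SD, PR, or CR at the end of a given cycle will continue to the next" cycle. The list of events that end therapy includes "2) confirmed PD, 3) clinical deterioration suggesting that no further benefit from treatment is likely". Its last item points to Sections 3.5 and 4.5.7.
- **Protocol 3.5.** The reasons for mandatory discontinuation include "Documented and confirmed disease progression as defined by RECIST or IWG criteria", "unless subject meets criteria for treatment beyond progression", with a reference to 3.5.1.
- **Protocol 3.5.1.** "Subjects will be permitted to continue on treatment beyond initial RECIST 1.1 defined PD", or beyond IWG-defined relapse or progression, "as long as they meet the following criteria". Six criteria follow. The section also requires that every decision to continue past initial progression be discussed with the Medical Monitor and that a risk/benefit assessment be documented.
- **SAP 4.2.1**, under best overall response (BOR): "A minority of subjects may continue treatment beyond confirmed progression or relapse, as described in Protocol Section 3.5.1".

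**The concern.** An end-of-cycle scan showing a first, not yet confirmed PD is a routine event in this population. At that visit the site must know whether the next cycle may start and what has to be in place beforehand. The sections differ on the triggering event (initial or confirmed progression) and on the conditions (two, or six plus the Medical Monitor step).

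What is at stake is mainly consent and subject protection. A full cycle contains 4 nivolumab and 2 urelumab doses (Protocol 3.1.2). A site could begin one in good faith under 3.1.2 while missing the written consent that 3.5.1 requires first. Sites that read different sections would also treat for different lengths of time after progression. The on-treatment list of programmed relevant deviations in SAP 7.2.3 has no item for dosing past progression without re-consent, so such cases could surface only through the separate listings of non-programmable deviations.

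**Working it through.** The plan gives no figure on this point, so the check compares the text for one case: a first, unconfirmed PD at the end of a cycle.

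| Source | Trigger | What it requires at this scan |
|---|---|---|
| Protocol 3.1.2, sentence on initial progression | Initial progression | 2 conditions: clinical benefit, tolerance |
| Protocol 3.1.2, next sentence | Unconfirmed PD | Continue; no condition stated in the sentence |
| Protocol 3.1.2, stopping list | Confirmed PD | Not yet a stopping event |
| Protocol 3.5 | Confirmed progression | No mandatory stop; 3.5.1 not yet invoked |
| Protocol 3.5.1 | Initial PD | 6 criteria, Medical Monitor discussion, documented risk/benefit assessment |
| SAP 4.2.1 | Confirmed progression | Describes 3.5.1 as applying from here |

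**Conditions.** The six criteria in 3.5.1 are:
1. clinical benefit without rapid progression;
2. all other eligibility criteria still met;
3. tolerance of study drug;
4. stable performance status;
5. no delay to an imminent intervention;
6. written consent before any further dose.

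The two conditions in 3.1.2 correspond to items 1 and 3, and item 1 only in part, since 3.1.2 does not mention rapid progression. That leaves 6 − 2 = 4 criteria absent from 3.1.2 (items 2, 4, 5 and 6), together with the Medical Monitor discussion and the documented assessment. The clinical-deterioration item in the 3.1.2 stopping list overlaps somewhat with item 4 but does not replace it.

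**Cross-references.** Section 3.1.2 does not cite 3.5.1. It cites 3.5, which mentions 3.5.1 only as an exception to stopping for confirmed progression. A reader who follows these references with an unconfirmed PD finds no reason to stop in 3.5 and is not sent on to the consent rule.

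**Where the texts collide.** For a subject who meets all six criteria and has re-consented, every section allows the next cycle. For a subject who has clinical benefit and tolerates the drug but has not re-consented, 3.1.2 says the subject goes on and 3.5.1 says no further dose may be given yet. This second case is the contradiction.

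**Effect on the analysis.** Protocol 3.5.1.1 dates progression at the initial event for subjects treated past RECIST-defined progression. SAP 4.2.1 cuts BOR for such subjects at the initial progression or relapse, and defines progression-free survival (PFS) by the first documented event. These hold whichever section a site follows. Last-dose date, exposure and the handling of deviations can still vary with the section followed.

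**The case against.** The strongest reply is that the requirements are cumulative. Section 3.1.2 is an overview, its sentence on continuing follows one that already restricts treatment past initial progression, and it refers to 3.5, of which 3.5.1 is a subsection. Section 3.5.1 is the specific text, is clear in its own terms, and is waived nowhere. A site that meets it breaches neither 3.5 nor the restriction in 3.1.2. Much of this stands: 3.1.2 is not unconditional, and a careful site that reads 3.5.1 will know what to do. It does not remove the problem, because the route from 3.1.2 through 3.5 reaches 3.5.1 only at confirmed progression, and the SAP describes 3.5.1 in the same way.

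A reader might go further on three points that the documents do not support.

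- *That Section 3.5 authorises dosing after unconfirmed PD.* It lists reasons to stop. Its silence on unconfirmed PD omits a mandatory stop and grants no permission.
- *That the primary safety endpoint is biased because the adverse-event window moves with an extra cycle.* The window runs to 100 days after the last dose for everyone, so it lengthens for any subject who continues, including one who meets all six criteria. SAP 7.6.6 also provides exposure-adjusted event rates.
- *That the number of affected subjects can be estimated.* The documents give no rate of PD at the first scan. Subjects who deteriorate clinically stop anyway, and those who meet 3.5.1 continue under every section. Only subjects dosed without meeting 3.5.1 matter, and they cannot be counted from these texts.

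Appendices 1 and 2, which set out the progression criteria, and the study schematic were not available for this check, so whether they clarify the meaning of confirmed progression is open.

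**Conclusion.** The inconsistency is in the current text and should be corrected. Protocol 3.5.1 applies from initial PD with six criteria, written consent and Medical Monitor discussion. Protocol 3.1.2 applies two of those conditions and treats confirmed PD as the stopping event, and Protocol 3.5 and SAP 4.2.1 bring in 3.5.1 only at confirmed progression. The consequence is a possible further dose after a first PD without the consent and safety conditions that 3.5.1 demands. How often this happened or would happen is unknown. The effect on efficacy results is small, because progression date, BOR and PFS rest on the initial or first documented event. The point does not threaten the validity of the trial. It is more than clerical because it concerns consent before dosing, and it stays live for the roughly 50 PD-L1 negative melanoma subjects still to be treated under these paragraphs. The conclusion rests on reading the four passages as written and on no numerical assumption.

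**What to change.** Reconcile Protocol 3.1.2, 3.5 and 3.5.1 so that one stated trigger, either initial or confirmed progression, leads to one list of conditions that includes the consent requirement. Put a direct reference to 3.5.1 in 3.1.2 beside the sentence on unconfirmed PD, and change the SAP 4.2.1 sentence to name the same trigger. Which trigger and which conditions apply is a clinical decision for the sponsor and investigators; this review takes no position on it.

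The cost is wording in three protocol paragraphs and one SAP sentence. No sample size, endpoint or analysis method changes.

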3.1.3 Clinical/Safety Follow-up

Subjects that discontinue the treatment phase will enter the Clinical/Safety Follow-up period. Subjects must be followed for at least 100 days after the last dose of therapy. Follow-up visits should occur at Days 30, 60 and 100 (\pm 7 days) after the last dose or coinciding with the date of discontinuation (\pm 7 days) if date of discontinuation is greater than 30 days after the last dose to monitor for adverse events. All subjects will be required to complete the 3 clinical safety follow-up visits regardless of whether they start new anti-cancer therapy, except those subjects who withdraw consent for study participation.

3.1.4 Survival/Long-Term Follow-up

After completion of the Clinical/Safety Follow-up period, all subjects will then enter the Survival/Long-Term Follow-up period. During this period, clinic visits or telephone contact every 3 months will be performed to assess survival status. The duration of survival follow-up will be 3 years following the first dose of study drug.

[figure not shown]
Subjects who discontinue study drug with ongoing SD, PR, or CR will continue to have tumor assessments completed every 12 weeks for the first year after discontinuation of study drug, and then continue to receive scans as per standard of care guidelines for follow-up or at a minimum of every 6 months up to 3 years following the first dose of study drug, or until disease progression or withdrawal of consent.

Subjects in the Survival/Long-term Follow-up period who have progression of disease will be allowed to receive tumor directed therapy as required.

Data from imaging assessments for subjects who have ongoing clinical benefit may continue to be collected after subjects complete the survival phase of the study.

A study schematic is presented below in Figure 3.1.4-1:

Figure 3.1.4-1: Study Schematic

CR = complete response; PR = partial response; SD = stable disease; PD = progressive disease

3.1.5 Dose Escalation

A 3+3+3 design will be used to assess the safety of urelumab given in combination with nivolumab. The cohorts for dose escalation are provided in [Table 3.1.5-1](#). The Dose Limiting Toxicity (DLT) observation period will last for 8 weeks following the first dose of study medication. The DLT evaluation period will be defined as 8 weeks after administration of the first combination dose of nivolumab and urelumab, and includes subjects who have had administration

of at least one dose of nivolumab monotherapy during this interval. This interval is based upon inclusion of the earliest times to onset of clinically significant adverse events attributed to study drug, and also allows for a substantial amount of time for unexpected toxicities related to the dosing regimen to emerge.

Approximately three subjects will be treated initially at each dose regimen. In order to assure a sufficient number of evaluable subjects in each cohort an additional subject may be added to a cohort (ie, enroll a fourth subject in a cohort of 3). For example, if 4 subjects are treated in the cohort, the decision to enroll additional patients or escalate will be made after the 3rd evaluable patient completes the DLT window. In this situation, if the decision is made to remain at the same dose level and the 4th patient is evaluable, he/she will be included as part of the 2nd cohort at that dose level.

Note: (i) Should this action be taken, cohort tolerability assessment and subsequent dose escalation, if indicated, will occur when the minimum number of evaluable subjects required to assess tolerability have completed the 8 week DLT period. (ii) If any additional subject experiences an event that would, per protocol, result in either cohort expansion or the halting of dose escalation, the escalation rules as defined below in [Table 3.1.5-2](#) will be followed.

Table 3.1.5-1: Dosages during Dose Escalation

Cohort	Total Subjects ^a	urelumab	nivolumab ^b
1	n = approximately 3-9	3 mg IV every 4 weeks	3 mg/kg or 240 mg IV every 2 weeks
2	n = approximately 3-9	8 mg IV every 4 weeks	3 mg/kg or 240 mg IV every 2 weeks
Total	n = approximately 6-18		

^a 3-9 subjects will be enrolled during dose escalation. Additional subjects may be added to each dose level for a total of up to 12 subjects per dose level

^b Nivolumab 3 mg/kg will be administered for subjects enrolled prior to Revised Protocol 02. Nivolumab 240 mg flat dose administered for subjects enrolled after Revised Protocol 02.

After dose escalation to the next cohort, 3-9 additional subjects may be enrolled in any previously tolerated (as defined by the dose escalation decision rules in [Table 3.1.5-2](#)) dose level (original 3-9 subjects from dose escalation plus additional subjects required to have a total cohort size of 12). If the rate of DLTs exceeds 33% in a given treatment regimen, the findings will be discussed and further enrollment may be interrupted for that specific treatment regimen and tumor type.

If one of the planned dose cohorts is determined to exceed the MTD, and/or based on ongoing safety/tolerability experience through the dose escalation phase of the study, an alternate dose escalation schema as outlined in [Table 3.1.5-3](#) may be explored in consultation and agreement between the Sponsor and investigators.

Sentinel Subject: During dose escalation, the first subject treated at each dose level will receive C1D1 (eg, the first dose of study drugs) and will be observed for 3 weeks such that one combination dose followed by one nivolumab dose are administered before additional subjects in the cohort receive the first dose of study drug (ie, C1D1).

Dose Escalation Rules: Table outlines the decision rules for dose escalation based on the number of subjects and observed DLTs. No intra-subject dose escalation or reduction is allowed. Subjects who withdraw from the study during the DLT period for reasons other than a DLT may be replaced within the same dose level/regimen. Dose escalation will be based on the number of dose limiting toxicities (DLTs) experienced during the DLT observation period.

If dose escalation is terminated, then the dose or dosing regimen below that which invoked the stopping rule will be declared the MTD.

Table 3.1.5-2: Decision Rules During Dose Escalation

Number of Evaluable Subjects/ Cohort	3-4 ^a			6-8			9-12	
Total Number of Observed DLTs	0	1	2 or more	1	2	3 or more	2	3 or more
Decision Rule	Dose Escalate	Enroll additional subjects in cohort to reach at least 6 subjects	Dose exceeds MTD	Dose Escalate	Enroll additional subjects at in cohort to reach at least 9 subjects	Dose exceeds MTD	Dose Escalate	Dose exceeds MTD

^a If 4 subjects are enrolled in a cohort, the decision to enroll additional patients or escalate will be made after the 3rd evaluable subject completes the DLT window. In this situation, if the decision is made to remain at the same dose level and the 4th subject is evaluable, he/she will be included as part of the 2nd cohort at that dose level

If either Cohort 1 or Cohort 2 exceeds the MTD, alternate treatment regimens may be explored during dose escalation or cohort expansion (listed in Table 3.1.5-3).

Table 3.1.5-3: Alternate Treatment Regimens

Cohort Designation	urelumab	nivolumab ^a
A ^b	8 mg IV every 8 weeks	3 mg/kg or 240 mg IV every 2 weeks
B ^b	8 mg IV every 8 weeks	1 mg/kg or 80 mg IV every 2 weeks
C	3 mg IV every 4 weeks	1 mg/kg or 80 mg IV every 2 weeks

Table 3.1.5-3: Alternate Treatment Regimens

Cohort Designation	urelumab	nivolumab ^a
D ^b	3 mg IV every 8 weeks	3 mg/kg or 240 mg IV every 2 weeks

^a Nivolumab 1 mg/kg or 3 mg/kg will be administered for subjects enrolled prior to Revised Protocol 02. Nivolumab 80 mg or 240 mg flat dose administered for subjects enrolled after Revised Protocol 02

^b Dosing regimen not applicable following Revised Protocol 03 (Dated 31-Aug-2015)

All available clinical and laboratory data observed during dose escalation will be reviewed to determine the alternative treatment regimen listed in [Table 3.1.5-3](#) to be evaluated. The nature, time of onset, and time to resolution of DLTs observed will be reviewed in the context of the current safety data from the respective urelumab and nivolumab trials. After review of this data, and after consultation between the investigators and the sponsor, the identified alternative treatment regimens may be evaluated.

